11.2.3. PK and PD Assessments

PK samples will be shipped to [REDACTED]. Details of the procedures to be followed for sample collection, storage, and shipment will be documented in a separate PK Laboratory Manual.

The following PK and PD assessments will be performed:

- Standard PK sampling: PK samples are to be taken predose or at 2 to 6 hours postdose following administration, as indicated in the Schedule of Events
- Plasma protein biomarker analysis (cytokines, chemokines, other inflammatory proteins)
- Total Igs: IgA, IgG, IgM

The bioanalytical assay for the determination of RPC1063 and its metabolites RP101075, RP101442, and RP101988 in K₂ EDTA human plasma utilizes a liquid/liquid extraction with ultra performance liquid chromatography (UPLC) separation and Tandem Mass Spectrometry (MS/MS) detection. Quantification is achieved using analyte peak area to internal standard peak area. For each analyte, a stable labeled version (tri-deuterium) was used as the internal standard. The method was validated for the concentration range of [REDACTED] (RPC1063 and RP101075), [REDACTED] (RP101442), and [REDACTED] (RP101988). The method was demonstrated to be selective, precise and accurate for analysis of RPC1063 and its metabolites in human plasma. The assay performance is not affected by hemolysis or lipemia.

RPC1063 and its metabolites were shown to be stable for at least 31 days at -70°C in human plasma and a long term stability program (-20°C and -70°C) is in progress.

CELGENE PROPRIETARY INFORMATION

CONFIDENTIAL

The information contained herein may not be used, disclosed, or published without the written consent of Receptos.

12. SAFETY DEFINITIONS, MONITORING, AND REPORTING

Throughout the study, the Investigator will remain alert to possible AEs. If an AE occurs, the first concern should be for the safety of the patient and appropriate medical intervention should be provided if necessary.

At the signing for the informed consent form, patients should be given names and telephone numbers of site staff for reporting AEs and medical emergencies.

12.1. Adverse Events (AEs)

The AE definitions and reporting procedures provided in this protocol comply with current CFR 21 Part 312. An AE is any untoward medical occurrence that does not necessarily have a causal relationship with the investigational medicinal product. An AE can therefore be any unfavorable or unintended sign, including an abnormal laboratory finding, symptom or disease temporally associated with the use of an investigational medicinal product whether or not considered related to the investigational medicinal product.

Relapses and MS disease progression will be monitored as study endpoints, but will not be recorded as AEs.

AEs will be monitored throughout the entire study. Investigators will ask the patient at each visit if they have experienced any untoward occurrence since the last study visit. All AEs will be recorded on the eCRFs provided: a description of the event, severity, time of occurrence, duration, any action (e.g. treatment and follow up tests) and the outcome should be provided along with the Investigator's assessment of the relationship to the study treatment.

AEs will be recorded from the start of study drug treatment until 28 days following the last dose of treatment with the study drug.

If known, the event diagnosis should be recorded rather than listing individual signs or symptoms. AEs must be graded as being mild, moderate or severe and their approximate duration given. Definitions of severity are as follows:

Mild: an AE usually transient in nature and generally not interfering with normal activities;

Moderate: an AE that is sufficiently discomforting to interfere with normal activities;

Severe: an AE that is incapacitating and prevents normal activities.

Even if the Investigator feels there is no relationship to the study drug, all AEs MUST be recorded in the eCRF. The Investigator is requested to assess the relationship of any AEs to treatment using the following definitions:

Unrelated: those AEs which are clearly and incontrovertibly due to extraneous causes (concurrent drugs, environment etc.) and do not meet the criteria for drug relationship listed under Unlikely, Possible, Probable or Related.

Unlikely: an AE may be considered unlikely if it includes at least the first two features:

- It does not follow a reasonable temporal sequence from administration of the drug.

- It could readily have been produced by the patient's clinical state, environmental or toxic factors, or other modes of therapy administered to the patient.
- It does not follow a known pattern to the suspected drug.
- It does not reappear or worsen when the drug is re-administered.

Possible: an AE may be considered possible if it includes at least the first two features:

- It follows a reasonable temporal sequence from administration of the drug.
- It could readily have been produced by the patient's clinical state, environment or toxic factors, or other modes of therapy administered to the patient.
- It follows a known response pattern to the suspected drug.

Probable: an AE may be considered probable if it includes at least the first three features:

- It follows a reasonable temporal sequence from administration of the drug.
- It could not be reasonably explained by the known characteristics of the patient's clinical state, environmental or toxic factors or other modes of therapy administered to the patient.
- It disappears or decreased on cessation or reduction in dose. There are exceptions when an AE does not disappear upon discontinuation of the drug (e.g. bone marrow depression, fixed drug eruptions, tardive dyskinesia, etc).
- It follows a known pattern of response to the suspected drug.

Related: an AE may be considered related if it includes all of the following features:

- It follows a reasonable temporal sequence from administration of the drug.
- It could not be reasonably explained by the known characteristics of the patient's clinical state, environmental or toxic factors or other modes of therapy administered to the patient.
- It disappears or decreased on cessation or reduction in dose. There are exceptions when an AE does not disappear upon discontinuation of the drug. For example: bone marrow depression, fixed drug eruptions, tardive dyskinesia, etc.
- It follows a known pattern of response to the suspected drug.
- It reappears or worsens if the drug is re-administered.

12.2. Serious Adverse Events (SAEs)

An SAE is any untoward medical occurrence or effect that fulfills the following criteria:

- Results in death
- Is life-threatening (NOTE: the term "life-threatening" refers to an event in which the patient was at risk of death at the time of the event; it does not refer to an event which hypothetically might have caused death if it were more severe)
 - Requires hospitalization or prolongation of existing inpatient hospitalization

requested and applicable. For unrelated cases, a full detailed case description may negate the need for additional hospital case records, discharge summaries etc.

12.4. Monitoring of Patients with Adverse Events

Investigators must carefully monitor each patient for AEs. This includes clinical laboratory variables. Assessments must be made of the seriousness, severity and relationship to the administration of the study treatment. After the initial AE/SAE report the Investigator is required to follow up proactively each patient and provide further information to [redacted] on the patient's condition. During the study all AE/SAEs should be followed up to resolution unless the event is considered by the Investigator to be unlikely to resolve due to the patient's underlying disease, or the patient is lost to follow up.

Monitoring of Patients with Adverse Events of Special Interest

Several of the AEs noted in fingolimod clinical studies may be a consequence of S1P1R stimulation and will therefore be closely monitored in the RPC01-201 study. These AEs include:

- a. Bradycardia and heart conduction abnormalities. Dose-related transient, reversible bradycardia, symptomatic bradycardia, and first, second, or higher degree atrioventricular block were reported primarily as first dose effects in fingolimod studies. The heart rate reduction observed with sphingosine-1-receptor agonists is an expected effect of S1PR modulation and appears to be conducted through the same pathway as vagus nerve stimulation. In addition, these negative chronotropic effects of S1P1R agonists appear to attenuate over time secondary to S1PR desensitization and internalization on cardiac myocytes (Kovarik 2008). This effect appears to occur with increasing exposures of study drug, thus gradual titration of the dose of RPC1063 over several days may mitigate against larger reductions in HR.
- b. Pulmonary toxicity. An initial sharp decrease followed by a slow progressive decline over time in FEV₁ was observed in fingolimod clinical studies. Nonclinical toxicity studies with RPC1063 have revealed the potential for pulmonary toxicity at doses considerably higher than the pharmacologically active dose. FEV₁, FVC, and DLCO will be measured in all patients. Every patient whose PFTs are abnormal will be followed until such time as resolution is confirmed or no further improvement is expected by the investigator (based on a follow-up period of not less than 3 months).
- c. Hepatotoxicity. Fingolimod caused frequent, reversible liver enzyme elevations greater than 3-fold above the upper limit of normal in up to 12% of patients; this was a significant cause of cessation of therapy. In this study, clinical chemistry analyses to assess LFTs will be performed. Every patient whose LFTs are abnormal will be followed until values return to baseline.
- d. Macular edema. Instances of serious macular edema were reported in fingolimod renal transplant studies, and a 0.8% incidence was reported as an SAE in fingolimod (1.25 mg dose) MS clinical studies. Nonclinical studies with RPC1063 have not revealed eye-related toxicities. In this study, measurement of central foveal thickness by OCT will be performed in all patients. For patients

with abnormal OCT findings or with visual signs or symptoms of macular edema, a general ophthalmologic examination including eye history, visual acuity, and dilated ophthalmoscopy will also be performed. Every patient whose ophthalmic evaluations reveal abnormalities will be followed until values return to baseline or no further improvement is expected by the investigator (based on a follow-up period of not less than 3 months).

Overall, the following procedures should be followed:

- Vital signs will be assessed in supine and standing position at every visit. A sudden, significant fall in blood pressure (> 20 mmHg) between 2 and 5 minutes after standing from the supine position will be interpreted as an orthostatic hypotension and will be documented in the patient chart and eCRF.
- Patients will be closely monitored in the clinic after their first dose of the initial dose titration regimen for a period of 6 hours after treatment. ECGs will occur predose and at Hour 6 following dosing, with more frequent assessments as clinically indicated; vital signs, including orthostatic blood pressure assessment, will be assessed predose and then hourly for 6 hours following dosing. See the monitoring guidelines in [Section 10.2.1.1](#) for further details.
- Clinicians should be particularly mindful of patients who have a low pulse at baseline (spontaneously or through drug induced β -receptor blockade), prior to administration of the study drug. Atropine IV is recommended as the first line treatment of bradycardia, up to a maximum daily dose of 3 mg. Furthermore, the common guidelines for treatment of bradycardia (e.g. Advanced Cardiac Life Support-ACLS guidelines) should be followed as appropriate:
 - In case of clinical symptoms or hypotension, administration of atropine 1 mg, repeated administration in 3-5 minutes.
 - If heart rate and/or blood pressure remains unresponsive, consider administration of dopamine drip 5-20 μ g/kg/min or epinephrine drip 2-10 μ g/min.
 - Performance of transcutaneous pacing may also be considered
 - In the setting of decreased blood pressure, isoproterenol should be avoided or used with caution.
- Any condition that might affect the outcome of pulmonary function testing (FEV₁ and FVC) including infection, respiratory symptoms, occupational exposures (including asbestos) and cigarette smoking, needs to be collected before every PFT testing and transcribed to the pulmonary function tests eCRF page. If patients have decline in PFT values (FEV₁ and/or FVC) below 50% of the predicted values, treatment should be discontinued. If a patient discontinues due to respiratory AE, the Investigator should ensure that the patient has adequate evaluations as clinically indicated by a pulmonologist (consider pulmonary function tests, chest X-ray or high resolution computed tomography, based on findings of the other exams) at the time of the AE. For patients with pulmonary nodules, lung biopsy should be considered (Cryptococcus pneumonia and pulmonary TB have been reported with fingolimod). Further evaluations will be conducted until such time as resolution is confirmed or no

CONFIDENTIAL

The information contained herein may not be used, disclosed, or published without the written consent of Receptos.

further improvement is expected by the investigator (based on a follow-up period of not less than 3 months).

- If patients have elevations in the LFTs (SGPT/ALT or/and SGOT/AST) greater than 3 times the ULN, a retest must be performed within 14 days. Upon confirmation of the abnormality, retests should be performed weekly until the elevated LFT decreases to below 3 times the ULN. If the LFT increase is confirmed to be above 5 times the ULN the study medication must be permanently discontinued.
- Study drug must be discontinued in any patient who has a diagnosis of macular edema that is of new onset or worsened since baseline. Patients with a diagnosis of macular edema must be followed up monthly and more frequently if needed based on the ophthalmologist's judgment. Further ophthalmological evaluations will be conducted until such time as resolution is confirmed or no further improvement is expected by the ophthalmologist (based on a follow-up period of not less than 3 months). If the patient does not show definite signs of improvement on examination 6 to 8 weeks after discontinuation of study drug, then therapy for macular edema in conjunction with an ophthalmologist experienced in the management of this condition should be initiated.
- The treating investigator will complete a dermatological (skin) examination for monitoring of the potential development of new cutaneous malignancies during the study. Patients with any suspicious finding noted during the examination will be referred to an appropriately qualified dermatologist for evaluation and treatment, if warranted. Dermatology examinations will be performed at screening, at 6 months for Part A, at 12 months and 24 months for Part B. For patients who discontinue treatment early, a dermatological (skin) examination will be performed at end of treatment.

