9.4.4. Withdrawal of Patients from Study Medication and/or the Study

9.4.4.1. Discontinuation of Study Medication

Reasons for discontinuation include, but are not limited to the following:

- Investigator decision

The Treating Investigator may discontinue study medication if it is determined that it is not safe or in the patient's best interest to receive further treatment. The Medical Monitor should be promptly notified of the decision.

- Noncompliance: after consultation between the investigator, the Medical Monitor, or Study Monitor, and the sponsor when appropriate, a patient may be discontinued from study medication for failure to comply with protocol requirements
- Intercurrent illness: A patient may be discontinued from study medication if, in the judgment of the treating investigator, the patient develops an intercurrent illness or complication that is not consistent with the protocol requirements or that, in any way, justifies discontinuation of study medication.
- Protocol-defined adverse events of special interest (see [Section 12.4](#)):
 - Confirmed AST or ALT >5 times the upper limit of the normal range, confirmed upon retest within 14 days of the original lab value (unless determined by the investigator to not be of hepatic origin)
 - A diagnosis of macular edema, which is new or worsening since baseline
 - FEV1 or FVC <50% of predicted values
- If the patient becomes pregnant
- Sponsor termination or suspension of the study

All patients who discontinue study medication should complete an Early Termination Visit (see [Table 2 \[Part A\]](#) and [Table 4 \[Part B\]](#)). Unless the patient withdraws consent or is lost to follow-up, they will be asked to undergo a follow-up visit 4 weeks after the last dose for the collection of safety data including lymphocyte recovery and to assess their disease status. Alternative treatment for multiple sclerosis (with the exception of medication given in the context of another clinical trial) can be started, if needed, after the early termination visit.

The reason for discontinuation of study medication will be recorded in the clinical records and the patient's eCRF.

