12.5. Procedures to be Followed in the Event of Abnormal Laboratory Test Values

In the event of unexplained abnormal laboratory test values, the tests should be repeated immediately and followed up until they have returned to the normal range and/or an adequate explanation of the abnormality is found. Abnormal laboratory values or test results constitute AEs only if they induce clinical signs or symptoms, are considered clinically significant, or require therapy. For abnormal laboratory test values related to AEs of special interest refer to [Section 12.4](#).

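### The liver stopping rule has a non-hepatic exception in Protocol Section 9.4.4.1 but none in Section 12.4, and nothing says which section governs

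*Protocol*

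**What the plan says.** Two sections of the current protocol (Version 4.0) say when a raised transaminase ends treatment.

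- **Section 12.4** defines the liver function tests by enzyme (ALT and/or AST). A value above 3 times ULN calls for a retest within 14 days and, once confirmed, weekly retests until the value is below 3 times ULN. It then says: "If the LFT increase is confirmed to be above 5 times the ULN the study medication must be permanently discontinued".
- **Section 9.4.4.1** opens with "Reasons for discontinuation include, but are not limited to the following". Under adverse events of special interest, where it refers the reader to Section 12.4, it lists AST or ALT above 5 times ULN confirmed on retest within 14 days, with the qualification "unless determined by the investigator to not be of hepatic origin".

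Section 12.5 also sends the reader to Section 12.4: "For abnormal laboratory test values related to AEs of special interest refer to" that section. Section 9.1.2.5 does the same for details of monitoring these events. The Part A SAP contains no stopping rule. It only tabulates liver test elevations up to the category of 5 times ULN or more (Section 10.2.2) and adverse events leading to permanent discontinuation (Section 10.1.5).

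**The concern.** One section gives the investigator a judgement that takes a patient out of the liver stopping criterion. The other requires a permanent stop and leaves no room for that judgement. A site that keeps dosing in good faith under Section 9.4.4.1 breaches Section 12.4, and Section 16.3 requires the protocol's instructions to be followed. Another site, reading Section 12.4, would stop drug in the same kind of patient.

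The stakes are patient safety and consistent conduct across the approximately 100-125 planned sites. The protocol names liver enzyme elevation as an event of special interest, and Section 12.4 records that fingolimod caused reversible elevations above 3 times ULN in up to 12% of patients. The exception comes with no criteria, and Section 9.4.4.1 does not ask for its basis to be recorded. Inconsistent stopping could also add some noise to the count of adverse events leading to discontinuation. It would not affect alpha, power or the primary analysis.

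**Working it through.** No arithmetic applies beyond a count, so the check is a comparison of the texts.

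**Step 1: the liver criterion, element by element.**

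| Element | Section 9.4.4.1 | Section 12.4 | Agree? |
|---|---|---|---|
| Enzymes | AST or ALT | ALT and/or AST | Yes |
| Threshold | above 5 times ULN | above 5 times ULN | Yes |
| Confirmation | retest within 14 days | retest within 14 days of a value above 3 times ULN; increase confirmed | Yes |
| Exception | "unless determined by the investigator to not be of hepatic origin" | none | **No** |
| Force | an item in an open list of reasons | mandatory and permanent | Mandatory wording only in 12.4 |

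**Step 2: a test case.** Take a confirmed ALT of 6 times ULN that the investigator judges non-hepatic. Under Section 9.4.4.1 the criterion is not met. Under Section 12.4 the patient must stop permanently. Stopping drug is consistent with both sections; continuing is not.

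**Step 3: can the word LFT in Section 12.4 imply a hepatic source?** No. That section defines the term by the two enzymes alone.

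**Step 4: the other special-interest stopping criteria found in both sections.**

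| Criterion | Section 9.4.4.1 | Section 12.4 | Trigger agrees? |
|---|---|---|---|
| Macular edema | "A diagnosis of macular edema, which is new or worsening since baseline" | "Study drug must be discontinued in any patient who has a diagnosis of macular edema that is of new onset or worsened since baseline" | Yes |
| FEV1 or FVC | "FEV1 or FVC <50% of predicted values" | "below 50% of the predicted values, treatment should be discontinued" | Yes |
| ALT or AST above 5 times ULN | with the non-hepatic exception | without it | **No** |

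Two of the three triggers match and one differs. This compares triggers only; the strength of the instruction also varies within Section 12.4 (must for liver and macular edema, should for lung function).

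**Step 5: is precedence stated?** Sections 9.1.2.5, 9.4.4.1 and 12.5 point to Section 12.4. None says that it prevails where the sections differ, or that the exception has no effect there. Section 16.3 requires adherence but does not rank the sections.

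**Step 6: how many patients?** This would need the rate of confirmed ALT or AST above 5 times ULN on the study drugs and the share judged non-hepatic. The documents give neither, so no number can be derived. The fingolimod figure concerns another drug and a lower threshold.

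**The case against.** The strongest reply is that the two texts can be read together. The Section 9.4.4.1 list is expressly open, so a case excluded from one item may still have to stop for a reason given elsewhere. No words there authorise continued dosing. The pointers all lead to Section 12.4, which holds the only mandatory wording. On that reading all that is missing is a precedence clause.

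The observation about the pointers is fair, and they do lean that way. But the joint reading leaves the exception with nothing to do: if Section 12.4 always requires a stop, the investigator's judgement under Section 9.4.4.1 never changes the outcome. Either the exception is dead text or the unconditional rule is wrong, so one of them has to change.

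Four further points deserve weight.

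- **Safeguards.** Weekly retests until below 3 times ULN, follow-up until values return to baseline, the investigator's discretion to stop on safety grounds and review by the data monitoring committee all remain. They limit the harm but do not settle which instruction applies.
- **Size.** No figure in the documents supports calling the affected group large or small. That stands; the group can be described only as the subset of confirmed rises judged non-hepatic.
- **The count of three.** It describes the text and does not measure the effect on patients. That also stands.
- **Intent.** The documents do not show whether the sponsor meant to have the exception, so the fix has to offer both routes.

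**Conclusion.** The concern holds. Two current provisions give incompatible instructions for a patient whose confirmed ALT or AST exceeds 5 times ULN and is judged non-hepatic, and nothing resolves the conflict. It affects one of the three special-interest stopping criteria shared by the two sections, and within that criterion only rises judged non-hepatic. There is no effect on alpha, power or the primary analysis. The conclusion rests on the wording alone and needs no assumption about event rates. It should be corrected because it concerns a mandatory safety stopping rule.

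**What to change.** State the liver rule once, in Section 12.4, and have Section 9.4.4.1 defer to it without restating its terms. There are two ways to settle the content:

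1. **Default: delete the parenthetical exception from Section 9.4.4.1.** This follows the only mandatory text and is the more cautious choice. The downside is that patients with non-hepatic rises stop drug permanently.
2. **If the sponsor intends the exception:** add the same words to Section 12.4 and require the investigator to document why the rise is judged non-hepatic.

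The cost is about one sentence in the next amendment. The change is not administrative, so under Section 16.2 it needs written approval from the regulatory authorities and the IRB/IEC. Under the default, each patient who stops has an Early Termination Visit. The follow-up visit 4 weeks after the last dose is already planned for every patient under Section 10.6. No statistical analysis changes.
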